Appendix 3: Mayo Score (Ulcerative Colitis)

Components of the Mayo Score	
Stool frequency	
0	Normal
1	1–2 stools/day more than normal
2	3–4 stools/day more than normal
3	5 or more stools/day more than normal
Rectal bleeding	
0	None
1	Visible blood with stool less than half the time
2	Visible blood with stool half of the time or more
3	Passing blood alone
Mucosal appearance at endoscopy	
0	Normal or inactive disease
1	Mild disease (erythema, decreased vascular pattern, mild friability)
2	Moderate disease (marked erythema, absent vascular pattern, friability, erosions)
3	Severe disease (spontaneous bleeding, ulceration)
Physician rating of disease activity	
0	Normal
1	Mild
2	Moderate
3	Severe

Appendix 4: Follow-up Headache questionnaire

Subject ID: _____ DOB: _____ Date: _____

Please describe your headaches:

1. How long after taking the study medication does your headache start?

 within 30 minutes within 60 minutes 1-2 hours 3-4 hours > 4 hours

[figure not shown]
2. How frequent are your headaches?

 less than 1 per day once or twice a day 3 times a day >3 times per day

3. How long do your headaches last in days?

 less 1 day 2 days 3 days 4 days 5 days 6 days 7 days >7 days than a day4. How severe are your headaches?
(on a scale of 0-10 with 10 being the most severe)
On average my headache would be a # _____ My most severe headache would be a # _____5. Do you have more than one type of headache?
 Yes No**If YES to above, please focus the following questions on your worst disability headache type*6. Using the image below as a guide, please check where your headaches are generally located
(circle left and/or right when indicated)

 Temple (R L)	 Back of head	 Front of head	 Ear (R L)
 Top of head (R L)	 Eye (R L)	 Neck	 Jaw
 Around head	 Other _____		

7. Your headaches are worse in the:

 morning	 afternoon	 evening	 during the night	 no pattern
-------------------------------	---------------------------------	-------------------------------	--	----------------------------------

8. Are your headaches worse lying down or standing? Lying down Standing

9. Do your headaches wake you up in the middle of the night? Yes No If yes, how often: _____?

10. Headache relief from medication: Do you take any medication to treat your headaches? If yes, Please, include all Over-The-Counter and Prescription medications you are using to treat your headaches:

Medication Name & dose	Average & Maximum used in 1 day	How many times weekly?

11.

11. Headache relief: without medication

After medication intake: within 1 hour 1-2 hours > 2 hours never became pain free after medication.

Duration of treatment: ≤ 1 day a few days < 1 week > 1 week never became pain free

12. Do you have other symptoms during your headache?

*mark all that apply

 nausea or upset stomach/vomiting	 sensitivity to smells	 Sensitivity to light (prefer a dark room)
 Difficulty thinking/concentrating/focus	 Sensitivity to sound (prefer a quiet room)	 Difficulty speaking/slurred speech
 Sore/stiff neck	 Increased urination	 Vision changes (blurred, spots, patterns)
 Anxiety	 Eye tearing in only ONE EYE	 Irritability
 Runny nose in only ONE NOSTRIL	 Memory problems	 Ringing in ears
 Increased appetite	 Decreased appetite	 Eye redness (R L Both)
 Drooping eyelid (R L Both)	 Diarrhea	 Swelling of eyelid (R L Both)
 Constipation	 Change in pupil (larger smaller)	 Insomnia
 Dizziness (lightheaded, woozy)	 Vertigo (the room appears to spin)	 Sleepiness
 Numbness/tingling (R L Both)	 Confusion	 Facial droop, droopy eyelid, unable to move one arm or leg
 Imbalance		

13. Do you have any of the following symptoms before your headache begins: (*check all that apply)

 Flashing lights	 Loss of vision in one eye	 Tunnel vision	 Spots: bright/dark
 Zigzag lines	 Loss of vision on one side	 Double vision	 Geometric forms
 Wavy lines	 Total blindness	 Distorted vision	 Numbness/tingling (R L Both)
 Speech difficulty	 Vertigo	 Dizziness/unsteadiness	 Light-headedness
 One-sided weakness (R L Both)	 Confusion / déjà vu / hallucinations	 Other: _____

## GLOSSARY OF ABBREVIATIONS

|       |   |
|-------|---|
| AE    | Adverse Event                               |
| AESI  | Adverse Event of Special Interest           |
| ALT   | Alanine Transaminase                        |
| AST   | Aspartate Transaminase                      |
| ATC   | Anatomical Therapeutic Chemical             |
| BLQ   | Below the Limit of Quantification           |
| BMI   | Body Mass Index                             |
| BUN   | Blood Urea Nitrogen                         |
| CI    | Confidence Interval                         |
| CPK   | Creatine Phosphokinase                      |
| CRA   | Clinical Research Associate                 |
| CRF   | Case Report Form                            |
| CRP   | C-Reactive Protein                          |
| CS    | Clinically Significant                      |
| CSR   | Clinical Study Report                       |
| D     | Day   |
| DBL   | Database Lock                               |
| DRM   | Data Review Meeting                         |
| DSMB  | Data Safety Monitoring Board                |
| E     | Number of Events in the Sample              |
| ECG   | Electrocardiogram                           |
| EoS   | End of Study                                |
| ESR   | Erythrocyte Sedimentation Rate              |
| gGT   | gamma-Glutamyl Transferase                  |
| GLDH  | Glutamate Dehydrogenase                     |
| GLS   | Global Longitudinal Strain                  |
| ICH   | International Conference on Harmonisation   |
| ICVSC | Independent Cardiovascular Safety Committee |

|           |  |
|-----------|--|
| ITT       | Intent-to-Treat Population                   |
| LDH       | Lactate Dehydrogenase                        |
| LLQ       | Lower Limit of Quantification                |
| LOCF      | Last Observation Carried Forward             |
| LS Mean   | Least Squares Mean                           |
| LVEF      | Left Ventricle Ejection Fraction             |
| M         | Month  |
| MMS       | Modified Mayo Score                          |
| MedDRA    | Medical Dictionary for Regulatory Activities |
| mg        | Milligram                                    |
| miR       | micro-RNA                                    |
| N         | Number of Patients in the Population         |
| n         | Number of Patients in the Sample             |
| NCS       | Not clinically significant                   |
| NRI       | Non-responder Imputation                     |
| NT-ProBNP | N-terminal pro-brain natriuretic peptide     |
| OC        | Observed Cases                               |
| o.d       | Once daily                                   |
| pMMS      | Partial Modified Mayo Score                  |
| pMS       | Partial Mayo Score                           |
| PT        | Preferred Term                               |
| TMS       | Total Mayo Score                             |
| QC        | Quality Control                              |
| QoL       | Quality of Life                              |
| RV        | Right Ventricle                              |
| SAP       | Statistical Analysis Plan                    |
| SAS       | Statistical Analysis System                  |
| SD        | Standard Deviation                           |
| SE        | Standard Error                               |
| SEM       | Standard Error of the Mean                   |
| SF-36     | Quality of Life Questionnaire                |

|         |  |
|---------|--|
| SOC     | System Organ Class                                 |
| TEAE    | Treatment Emergent Adverse Event                   |
| UC      | Ulcerative Colitis                                 |
| WBC     | White Blood Cell                                   |
| WHO-DDE | World Health Organisation Drug Dictionary Enhanced |

## 1 INTRODUCTION

### 1.1 GENERAL

This statistical analysis plan (SAP) describes the statistical methods to be used during the reporting and analyses of data collected under ABIVAX Protocol ABX464-102 and should be read in conjunction with the study protocol and case report form (CRF).

This version of the plan has been developed using the protocol Version 7.0 dated 07FEB2022 and CRF specifications dated 11JAN2022. Any further changes to the protocol or CRF will be reviewed for potential impact on the SAP which will be amended if it is deemed necessary.

At the time of writing this version of the SAP, recruitment is terminated, treatment is ongoing.

Draft 1 was reviewed by the Simbec-Orion project manager, medical writer and statistical reviewer. The analysis plan will be finalised and approved by the sponsor prior to unblinding of study treatment codes for the planned interim analysis and prior to database lock.

### 1.2 CHANGES FROM PROTOCOL

- The echocardiography secondary endpoints will be included in a separate report.
- Sustained clinical remission and sustained endoscopic remission/improvement will be summarized as part of the secondary endpoints.
- Observed Cases (OC) Set and Non-responder Imputation (NRI) Set are defined for populations instead of the populations defined in the protocol.
- In the definition of corticosteroid-free clinical remission (Section 11.3.1.6), time interval is changed from 12 weeks to 90 days for consistency with other Abivax studies.
- In the definition of clinical response (Section 11.3.1.6), Modified Mayo Score is used instead of Total Mayo Score for consistency with other Abivax studies.
- All efficacy variables will be summarized based on the following subgroups:
  - Patients being in clinical response at BOLS and not being in clinical response at BOLS
  - Patients previously treated with biological drugs and naive from biological drugs.
- In the Synopsis and Section 2.4 of the protocol, M24 is missing from the list of timepoints for clinical remission, clinical response, endoscopic improvement, endoscopic remission and corticosteroid-free clinical remission inconsistently with further sections. This timepoint is included in the current SAP to ensure that these secondary endpoints are analysed for all required timepoints.

### 1.3 CHANGES FROM PREVIOUS VERSIONS OF THE SAP

No previous versions of the SAP exist.

## 2 STUDY OBJECTIVES

### 2.1 PRIMARY OBJECTIVE

The primary objective of the study is to evaluate the long-term safety of ABX464 given at 50 mg once daily in subjects with Moderate to Severe Active Ulcerative Colitis.

### 2.2 SECONDARY OBJECTIVES

The secondary objectives are:

- To evaluate the long-term effect of ABX464 on clinical and endoscopic remission in subjects with Moderate to Severe Active Ulcerative Colitis assessed by the Mayo Score (MS);
- To evaluate the long-term effect of ABX464 on inflammatory markers (C-Reactive Protein (CRP), Calprotectin and Erythrocyte Sedimentation Rate (ESR));
- To evaluate the long-term of ABX464 on Quality of Life (QoL) measured by the Quality of Life Questionnaire (SF-36) questionnaire in subjects with Moderate to Severe Active Ulcerative Colitis until M24.

The echocardiography objective is to evaluate the effect of ABX464 on cardiac function as assessed through echocardiograms and will be included in a separate report.

## 3 STUDY DESIGN

### 3.1 OVERVIEW

This study is an open-label study aiming at evaluating the long-term safety and the efficacy profile of ABX464 given once a day (o.d) at 50 mg in subjects who have been previously enrolled in the ABX464-101 clinical study (induction study) and who are willing to continue their treatment.

All subjects receive ABX464 given at 50 mg o.d irrespective of their previous treatment received in the ABX464-101 study (i.e. ABX464 or Placebo). With respect to this, there will be 2 groups: 50mg ABX464 (101 study) + 50mg ABX464 (102 extension) and Placebo (101 study) + 50mg ABX464 (102 extension).

The actual treatment received by a subject throughout the previous study (ABX464-101) was not known at the time the subjects entered this follow-up study.

The enrolment in this follow-up study was based on the willingness of the subject to carry on his/her participation and also based on investigator's judgement.

Subjects are treated with ABX464 for an overall period of 48 months. Subjects are followed up weekly during the first month, every two weeks during the second month and then on a monthly basis until M24, then quarterly from M24 to M48.

At M48, depending on their clinical response, eligible patients willing to continue study treatment will be offered to take part into a long term follow up safety study (ABX464-108 study). ABX464-108 study is

a separate study requiring health authorities and ethics committees' approval. If patients are not eligible to pursue treatment in this long-term follow-up study, they will be followed for 4 additional weeks for safety purposes before End of study Visit.

### 3.2 INCLUSION AND EXCLUSION CRITERIA

To be eligible for inclusion into this study, each patient must fulfil all inclusion criteria and not violate any exclusion criteria (for the protocol under which they are entered). Patients must have completed the initial 2-month treatment phase (ABX464-101 study). Details of the inclusion and exclusion criteria are presented in the protocol and amendments.

### 3.3 STUDY TREATMENT

All subjects receive ABX464 50 mg o.d irrespective of their previous treatment received in the ABX464-101 study (i.e. ABX464 or Placebo). With respect to this, there will be 2 groups:

| ABX464-101 treatment |             | ABX464-102 treatment
(extension study) |
|----------------------|-------------|---|
| Group #1             | 50mg ABX464 | 50mg ABX464                               |
| Group #2             | Placebo     | 50mg ABX464                               |

### 3.4 STUDY TIMEPOINTS

Subjects were enrolled in the present study at Day (D) 0 and are treated for an overall duration of 48 months.

From ABX464 treatment stop onwards, subjects will be followed-up for 4 additional weeks.

| Visit | Visit          | Window    |
|-------|----------------|-----------|
| 1     | Screening/ D0  |           |
| 2     | D7             | ± 2 days  |
| 3     | D14            | ± 2 days  |
| 4     | D21            | ± 2 days  |
| 5     | D28            | ± 4 days  |
| 6     | D42            | ± 2 days  |
| 7     | D56/ M2        | ± 4 days  |
| 8     | Mx+1
to M24 | ± 4 days  |
| 9     | M27 to M48*    | ± 14 days |
| EoS   | EoS**          | ± 4 days  |

\*: Visits are performed quarterly after M24 (at M27, M30, M33, M36, M39, M42, and M48)

\*\*: End of Study visit: 28 days after ABX464 Stop

If more than one visit occurs within a window, the nearest to the scheduled time will be presented within the summaries.

See Section 16.1 for the Study Schedule.

### 3.5 SAMPLE SIZE CONSIDERATIONS

Not applicable. All patients in this study are those who were included in the ABX464-101 study.

### 3.6 RANDOMISATION

Not applicable. All the patients will receive ABX464 50mg o.d.

## 4 STUDY VARIABLES

### 4.1 PRIMARY VARIABLE

The primary endpoint of this study is defined as the number of incidences of treatment-emergent adverse events in the ABX464 treated subjects.

### 4.2 SECONDARY VARIABLES

The secondary endpoints of this study are:

---

Version Date 20 MAY 2021

Template STATt004

- The change from Day 0 in Total Mayo Score.
- The change from Day 0 in Partial Mayo Score.
- The time to Ulcerative Colitis (UC) worsening.
- The change from Day 0 in faecal calprotectin, CRP levels and ESR.
- The scores and changes from Day 0 in SF-36 Questionnaire scores.
- The micro-RNA (miR-124) expression at month 12, month 36 and month 48.
- The number of incidences of treatment-emergent serious adverse events.
- The number of incidences of treatment-emergent adverse events of special interest.
- The number of incidences of adverse events leading to investigational product discontinuation.
- The number of incidences of specific laboratory abnormalities.
- Clinical remission
- Corticosteroid-free clinical remission
- Clinical response
- Endoscopic improvement
- Endoscopic remission
- Sustained clinical remission and sustained endoscopic remission/improvement

The echocardiography secondary endpoints will be included in a separate report.

#### **4.3 PHARMACOKINETIC VARIABLES**

Pharmacokinetic variables are not evaluated in this study.

#### **4.4 PHARMACODYNAMIC VARIABLES**

Pharmacodynamic variables are not evaluated in this study.

#### **4.5 OTHER OUTCOME VARIABLES**

Not applicable.

#### **4.6 SAFETY VARIABLES**

Safety will be evaluated by the following:

- Adverse events
- Laboratory parameters
- Vital signs (body temperature, systolic and diastolic blood pressure, heart rate)
- Physical examination
- Electrocardiogram (ECG)

## 5 DEFINITIONS

### 5.1 DEFINITIONS

**Study Drug:** Study drug is taken to mean ABX464 50 mg o.d.

**Baseline:** Baseline is defined by patient and by variable as the last non-missing (including repeat or unscheduled) value before the first dose of study drug. 2 baselines will be defined:

- Baseline Induction Study (BIS): Day 0 of ABX464-101 study
- Baseline Open-Label Study (BOLS): Day 56 of ABX464-101 study

BIS is defined as a baseline for ABX464-101 (induction) study and BOLS is defined as a baseline for ABX464-102 (open-label) study.

Primarily, baseline without the study number refers to baseline of the current study (BOLS).

**Study Day:** Study day is the number of days since start of treatment for ABX464-102 study where the date of first dose is counted as 1.

**Treatment Exposure:** Treatment exposure is the number of days during the treatment period that the patient was exposed to the study treatment and is calculated as:

$$(\text{Date\_of\_last\_dose}) - (\text{Date\_of\_first\_dose}) + 1$$

**Compliance:** Compliance is the number of doses actually taken divided by the scheduled number of doses expressed as a percentage during the extension period or until early withdrawal.

**Non-compliance:** Non-compliance is defined as taking less than 80% or more than 120% of study medication during the extension period or until early withdrawal.

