1.3. Rationale for the clinical study and study design

Phase IIb study (ABX464-101) aimed at evaluating the efficacy and safety of ABX464 given at a fixed dose of 50mg once daily versus placebo in patients with moderate to severe active UC who have failed or are intolerant to immunomodulators, anti-TNF α or corticosteroids was conducted in Belgium, France, Germany, Austria, Poland, Hungary.

32 patients were randomized (23 ABX464 patients/9 placebo). The principal study results are presented below.

A strong efficacy signal was observed with ABX464 50 mg:

- Clinical Remission rate of 35.0 % of ABX464 patients (Placebo = 11.1%)
- Mucosal Healing rate of 50.0 % (p=0.03) of ABX464 patients (Placebo = 11.1%)
- Clinical Response rate of 70.0 % of ABX464 patients (Placebo = 33.0%)

Same results were also observed in Total and Partial Mayo Score, as depicted in the following graphs

[figure not shown]

Figure 3: Mean change in Total and Partial Mayo Score in ABX464-101 study

At the end of the completed 2 months induction treatment study, 22 Patients (15 previously treated with ABX464 and 7 on placebo) were enrolled into the open-label maintenance study with ABX464 50mg daily (ABX464-102) regardless of what treatment they had previously received. An interim analysis of this maintenance study was performed after all patients had completed at least 12 months dosing in the maintenance study, with a mean ABX464 treatment duration in the maintenance study of 422 days.

The interim analysis used the Month 12 Per Protocol (M12 PP) dataset which included all subjects that had a Month 12 visit. Of the 22 subjects, 3 subjects were excluded from the M12 PP Set: 2 subjects from the ABX464 induction group (one who withdrew due to lack of efficacy at M1 of the maintenance study and one who was lost to follow-up) and 1 subject from the placebo induction group (grade 2 headache at month 4), resulting in 19 subjects analyzed in the efficacy M12 PP set at baseline. Of the nineteen subjects in the set, sixteen had had a Month 12 endoscopy performed which forms part of the Total Mayo score (TMS).

Clinical remissions obtained at the end of the induction study were durable and the rates further improved during the maintenance phase, as additional subjects achieved clinical remission for 12 months treatment.

All patients who had an endoscopy performed, had an endoscopic sub-score of 0 or 1. 12/16 patients were in clinical remission at month 12.

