8.2. Definition of an AESI

The following events will be considered AESI and must be reported to Intuvigilance (same procedure as SAE).

Skin Lesions (regardless of its severity)

A dermatologist consultation should be scheduled to evaluate the type of lesion, its severity and etiology. An anonymized medical report shall be provided.

Headaches

Headaches are frequently reported by patients dosed with ABX464. Abivax follows closely, by means of individual adapted questionnaire, provided in Appendix #4, this AE in specific situations (i.e. headache lasting longer than 72 hours AND not resolved by standard painkillers).

Anemia

Some degree of anemia was found in the 9-month marmoset study with ABX464-N-Glu. Although it has not been reproduced clinically, Abivax performs surveillance for anemia by means of regular determination of hemoglobin and hematocrit levels. Anemia defined as Hb drop > 2 g/dL from baseline or Hb < 8g/dL will be reported as AESI.

Hepatic enzymes

ABX464 showed liver findings in some toxicological studies, hence attention is paid to identification of liver enzymes elevations in subjects. No human predictors of hepatotoxicity for ABX464 or its metabolite, ABX464-N-Glu, have been identified. Based upon preclinical and clinical available data, a DILIsym evaluation of ABX464 was conducted and concluded that there was no risk of DILI in these patients. A signal detection analysis of ALT/AST changes in subjects treated with ABX464 did not reveal any meaningful variation of the mean ALT/AST measurement throughout treatment nor an increased incidence of any liver function tests (LFTs). Sporadic cases of isolated alkaline phosphatase increase have been reported in patients dosed with ABX464.

A specific liver function monitoring plan is implemented in all clinical studies (see Section 5.3.10 and Section 7.2) during the course of treatment and a measurement of LFTs 4 weeks after treatment interruption (during End of Study visit). The LFTs should, as per the clinical protocols, include at least the determination of the liver transaminases (ALT/AST), gamma-glutamyl transferase (GGT), alkaline phosphatase and total bilirubin. Specifically, an increase $\geq 3.0 \times$ ULN in liver transaminases (AST/SGOT and/or ALT/SGPT) or an increase $\geq 2.0 \times$ ULN in total bilirubin without initial findings of cholestasis (elevated alkaline phosphatase) will be reported as AESI.

Severe (grade ≥ 3) infections and opportunistic infections

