#### 11.3.1.3 Faecal calprotectin, CRP levels and ESR

Absolute values and change from BIS and from BOLS to each post BOLS timepoint will be presented using descriptive statistics for faecal calprotectin, CRP and ESR levels (*Table 14.2.3.1 and 14.2.3.2*).

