### 11.6.2 Laboratory Data

The absolute values of each laboratory parameter (Hematology, Biochemistry) will be summarised at each visit along with the change from baseline to each post baseline timepoint (*Table 14.3.3.1 and 14.3.3.2*). In addition, shift tables from baseline to each post baseline timepoint will be presented (*Table 14.3.3.3 and 14.3.3.4*) to show Normal/ Abnormal Clinically Significant (CS)/ Abnormal Not Clinically Significant (NCS) results.

Laboratory data listings will be presented in two ways:

- Abnormal values (presented within the data summaries) (*Table 14.3.3.5*)

- All laboratory data (presented within the data listings)

If lab results are repeated at the same visit, the repeated result will be used in summaries (instead of the original one) provided the sample was taken within the visit window, otherwise the original result will be used. All results will be listed.

Lab results at unscheduled visits will be included in the listings but will not be summarised.

Serum pregnancy data will be listed only.

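### Most safety change and shift summaries start from Day 56 of induction, an on-drug value for 15 of 22 patients; add a pre-ABX464 reference beside it

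*SAP*

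**What the plan says.** SAP 5.1 gives a general rule and then a default. Under the rule, baseline is the "last non-missing (including repeat or unscheduled) value before the first dose of study drug", and the same section says "Study drug is taken to mean ABX464 50 mg o.d". It then names two baselines: BIS, which is Day 0 of the induction study, and "Baseline Open-Label Study (BOLS): Day 56 of ABX464-101 study". The default follows: "Primarily, baseline without the study number refers to baseline of the current study (BOLS".

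The safety sections name no study when they refer to baseline. Under SAP 11.6.2, laboratory values "will be summarised at each visit along with the change from baseline to each post baseline timepoint". SAP 11.6.3 (vital signs), 11.6.4 (physical examination) and 11.6.5 (ECG) are similar, and the shells for Tables 14.3.3.1 to 14.3.3.4, 14.3.4, 14.3.5 and 14.3.6 carry a single Baseline row.

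The efficacy sections use both references. SAP 11.3.1.3, on faecal calprotectin, CRP and ESR, says "Absolute values and change from BIS and from BOLS to each post BOLS timepoint will be presented", and the Mayo and SF-36 sections follow the same pattern.

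Protocol 1.3 gives the mix of prior treatment: "22 Patients (15 previously treated with ABX464 and 7 on placebo) were enrolled into the open-label maintenance study". Protocol 8.2 has two AESI rules that depend on a baseline. One is "Anemia defined as Hb drop > 2 g/dL from baseline or Hb < 8g/dL will be reported as AESI"; the other is a relative change above 20% in cardiac laboratory parameters. Neither says which baseline is meant.

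**The concern.** The primary objective is the long-term safety of ABX464. For patients randomised to ABX464 in induction, Day 56 is not a pre-treatment value. Protocol 1.2.5 reports that pharmacokinetic steady state is reached after 4 weeks, so these patients were fully exposed by then. If a laboratory value, vital sign or ECG status moved in the first 8 weeks and stayed there, change from BOLS would show nothing.

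The general rule in SAP 5.1, read literally, gives BIS for these patients, so the section does not agree with its own default. The SAP also gives efficacy a pre-drug reference and does not say why safety lacks one. Finally, the Total column pools change from an on-drug value in one group with change from a pre-drug value in the other.

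**Working it through.** **Inputs.** 22 patients, 15 from ABX464 and 7 from placebo (Protocol 1.3). Induction lasts 56 days and this study 48 months (SAP 3.1, 5.1). The haemoglobin rule is a drop above 2 g/dL, and the cardiac laboratory rule a change above 20% (Protocol 8.2). The documents give no induction change in any safety parameter, so the sizes below are assumptions. The study is descriptive and has no sample-size or power figure to reproduce.

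**1. Who is affected.** 15 + 7 = 22, which agrees with the stated enrolment. The on-drug share at BOLS is 15/22 = 68.2%. For the other 7/22 = 31.8%, BOLS precedes any ABX464.

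**2. How much follow-up is affected.** Only the induction period falls before BOLS. With calendar months, 48 months is 1,461 days, and 56/(56 + 1,461) = 3.7% of planned exposure. With 28-day months it is 56/(56 + 1,344) = 4.0%. This is a share of time. An early, persistent shift would lie wholly inside it.

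**3. Haemoglobin, assumed induction fall d.** To exceed a 2 g/dL drop from BOLS, the total fall from BIS must exceed 2 + d. If the 15 patients fall by d on average in induction, the Total-column mean change from BOLS omits (15/22) × d relative to change from each patient's pre-ABX464 value.

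| d (g/dL) | Fall from BIS needed (g/dL) | Omitted from Total mean (g/dL) |
|---|---|---|
| 0.5 | more than 2.5 | 0.34 |
| 1.0 | more than 3.0 | 0.68 |
| 1.5 | more than 3.5 | 1.02 |

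For one hypothetical patient with 13.0 at BIS, 11.2 at BOLS and 9.4 later, the steps are −1.8 and −1.8 and the total is −3.6 g/dL. The BOLS value meets the eligibility limit (above 9.0 g/dL). Neither the 2 g/dL drop from BOLS nor the 8 g/dL floor is reached.

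**4. The opposite direction.** If haemoglobin rises by 1.0 g/dL in induction as colitis improves, d = −1.0, and a fall of more than 2 − 1.0 = 1.0 g/dL from BIS is enough. BOLS is then the more sensitive reference.

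**5. Cardiac markers, assumed induction rise r.** To exceed 20% from BOLS, the rise from BIS must exceed 1.2 × (1 + r) − 1. For r = 5%, 10% and 20% this gives 26%, 32% and 44%. For NT-proBNP the calculation does not apply: the flow chart schedules it only at M42, M48 and end of study, so no BOLS value is planned.

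**The case against.** Using the current study's own entry value is a defensible convention for an extension, and SAP 5.1 states it openly. Protocol 5.3.5 likewise compares ECG findings with an ECG from the end of ABX464-101. Much also remains visible without a BIS reference:

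- Laboratory and vital-sign values and ECG status are summarised by visit, and abnormal laboratory values are listed with reference ranges (Table 14.3.3.5). The hypothetical 9.4 g/dL would appear there if it were below the local range, and would be an adverse event if judged clinically significant.
- The AESI limits for transaminases, bilirubin, lipase and amylase, and the 8 g/dL haemoglobin floor, need no baseline.
- The placebo/ABX464 group has its own column, a pre-drug baseline and frequent visits in its first 8 weeks on ABX464.

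All of this stands, and it limits the point. It does not supply the missing item: within-patient change from a pre-ABX464 value in the larger group.

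A reader might infer three stronger things that the documents do not support.

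- *Every safety change runs from an on-drug value.* CRP and ESR also have change from BIS, echocardiography endpoints use the previous echocardiogram, and NT-proBNP has no planned BOLS value. Applying BOLS to the Protocol 8.2 AESI rules is an inference from the SAP default.
- *Cumulative effects are hidden from the primary endpoint.* That endpoint is a count of treatment-emergent adverse events. Baseline reaches it only indirectly, through findings judged against baseline and because events that began in induction count only if they worsen. Accumulation from Day 56 to M48 is shown in all patients.
- *The summaries are biased toward no effect.* That would need induction shifts to be adverse and in the same direction as later ones. BIS was taken in active disease, no induction safety changes are given, and step 4 of the working shows the opposite can occur.

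**Conclusion.** The point holds as a gap in presentation. For 15 of 22 patients (68%), the change and shift summaries for laboratory parameters (CRP and ESR apart), vital signs, physical examination and ECG leave out whatever moved in the first 8 weeks on ABX464. The general rule in SAP 5.1 would give BIS for these patients, and the SAP already gives efficacy that reference. The baseline for the relative haemoglobin and cardiac laboratory AESI rules is also unstated.

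The size and direction of any effect cannot be known from the documents; the haemoglobin and cardiac-marker figures only illustrate the mechanism. The enrolment split is the one firm number. The conclusion rests on reading the unqualified baseline in SAP 11.6.2 to 11.6.5 as BOLS, as SAP 5.1 directs. BIS should supplement BOLS and not replace it, because change from BIS mixes drug effect with change in colitis activity.

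**What to change.** Amend the SAP before database lock, as Protocol section 9 allows:

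1. In SAP 5.1, reconcile the general baseline rule with the BOLS default, and define a pre-ABX464 value for safety: BIS for the ABX464/ABX464 group and BOLS for the placebo/ABX464 group.
2. Keep all BOLS-based summaries. For the ABX464/ABX464 group, add change and shift from BIS in Tables 14.3.3.1 to 14.3.3.4, 14.3.4 and 14.3.6, and in 14.3.5 where ABX464-101 Day 0 data exist. The placebo/ABX464 group needs no new rows.
3. Add a supplementary count, by group, of patients whose haemoglobin falls more than 2 g/dL from the pre-ABX464 value.
4. State which baseline each relative AESI summary uses (haemoglobin and cardiac laboratory), and what applies to NT-proBNP, which has no scheduled BOLS value.
5. Leave the Total column on BOLS. A Total mixing BIS and BOLS would pool change since active disease before induction with change since the end of 8 weeks on placebo, and at M12 would combine about 14 and 12 months on drug.

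The cost is SAP wording, extra rows and a footnote that change from BIS also reflects disease activity. No new patient assessments are needed. The main dependency is whether Day 0 haematology, biochemistry, vital signs and ECG from ABX464-101 can be merged. The efficacy tables already plan such a merge for CRP and ESR, but the documents do not show that the full safety panel was collected at Day 0.
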